Final Month (last 28 days prior to and including the Reference Day)	Subject did not bleed during the last 28 days prior to and including the Reference Day

Incidence and cumulative incidence of amenorrhea at each month will be reported using the categories specified in in [Table 10](#).

The summary will be provided in the following 2 ways: (1) including only subjects who have at least 155 days (lower bound of Month 6 visit window as in [Table 1](#)) on study drug prior to and including the Reference Day. The denominator is the number of subjects who have at least 155 days on study drug prior to and including the Reference Day. (2) LOCF: including all subjects who have at least 38 days on study drug prior to and including the Reference Day. If a subject meets the criteria for amenorrhea but discontinues, this subject's amenorrheic status was carried forward to the time points after the subject has

discontinued study drug. The denominator is the number of subjects who have at least 38 days on study drug prior to and including the Reference Day.

Plots will be provided by treatment group for percentage of subjects with incidence and cumulative incidence of amenorrhea during the Treatment Period, respectively.

Table 10. Categorical Summary of Incidence and Cumulative Incidence of Amenorrhea

Analysis	Time Interval	Numerator Calculation
Incidence	Month 2 (≤ Study Day 56)	Last bleeding/spotting day occurred during Study Days 1 – 28 and continued not bleeding/spotting every day thereafter until and including the Reference Day
	Month 3 (Study Day 57 – 84)	Last bleeding/spotting day occurred during Study Days 29 – 56 and continued not bleeding/spotting every day thereafter until and including the Reference Day
	Month 4 (Study Day 85 – 112)	Last bleeding/spotting day occurred during Study Days 57 – 84 and continued not bleeding/spotting every day thereafter until and including the Reference Day
	Month 5 (Study Day 113 – 140)	Last bleeding/spotting day occurred during Study Days 85 – 112 and continued not bleeding/spotting every day thereafter until and including the Reference Day
	Month 6 (Study Day 141 – 168)	Last bleeding/spotting day occurred during Study Days 113 – 140 and continued not bleeding/spotting every day thereafter until and including the Reference Day
	Cumulative	Month 2 (≤ Study Day 56)
Month 3 (Study Day 57 – 84)		Last bleeding/spotting day occurred before Study Day 57 and continued not bleeding/spotting every day thereafter until and including the Reference Day
Month 4 (Study Day 85 – 112)		Last bleeding/spotting day occurred before Study Day 85 and continued not bleeding/spotting every day thereafter until and including the Reference Day
Month 5 (Study Day 113 – 140)		Last bleeding/spotting day occurred before Study Day 113 and continued not bleeding/spotting every day thereafter until and including the Reference Day
Month 6 (Study Day 141 – 168)		Last bleeding/spotting day occurred before Study Day 141 and continued not bleeding/spotting every day thereafter until and including the Reference Day

11.3.2.2 Suppression of Bleeding

Suppression of bleeding is defined similarly to amenorrhea as in Section 11.3.2 except that spotting is allowed. For each subject, achieving suppression of bleeding is defined as having 0 days of bleeding during the last 28 days prior to and including the Reference

Day with the interval starting from Study Day 11. The suppression of bleeding analysis will include subjects with at least 38 days prior to and including the Reference Day. If a subject did not have evaluable AH data during the last 28 days and no bleeding was indicated on UBQ ("Subject only has spotting that did not require the use of sanitary products" or "There was no visible blood on the sanitary products" was allowed), then the subject is considered having achieved suppression of bleeding.

The number and percentage of subjects achieving suppression of bleeding will be summarized by treatment group and will be compared between each of the elagolix dose groups and placebo using a Pearson's chi-square test or Fisher's exact test (if $\geq 20\%$ of the cells have expected counts less than 5).

Time to suppression of bleeding is defined as the number of days from the first study drug dose date to the day a subject achieving suppression of bleeding (i.e., the day a subject achieving suppression of bleeding – the first study drug dose date + 1). For a subject who achieved suppression of bleeding, the day she achieved suppression of bleeding is defined as the next day of the last bleeding day during the Treatment Period. The median, Q1, and Q3 of time to suppression of bleeding will be calculated using Kaplan-Meier method.

Monthly analysis of bleeding for suppression of bleeding, incidence and cumulative incidence of suppression of bleeding will be provided in the same way as was done for amenorrhea in [Table 9](#) and [Table 10](#). Plots will be provided by treatment group for percentage of subjects with incidence and cumulative incidence of suppression of bleeding during the Treatment Period, respectively.

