5.4 Removal of Subjects from Therapy or Assessment

Each subject has the right to withdraw from the study at any time. In addition, the Investigator may discontinue a subject from the study at any time if the Investigator considers it necessary for any reason, including the occurrence of an adverse event or noncompliance with the protocol. Subjects who withdraw from the study will not be replaced unless it is mutually agreed upon, in writing, by the Investigator and AbbVie. Each subject will be withdrawn from the study if any of the following occur:

- The subject decides to withdraw consent for any reason.
- The investigator believes it is in the best interest of the subject.
- Clinically significant deterioration of the subject's medical status as determined by the investigator.
- The subject requires surgical intervention for treatment of uterine fibroids and menstrual bleeding or other procedures including hysterectomy, myomectomy, uterine artery embolization, high intensity focused ultrasound (HIFU), endometrial ablation, dilation and curettage (D&C), etc. during the Treatment Period. In the post treatment period these procedures do not warrant withdrawal if performed during the Post-Treatment Period unless a hysterectomy with bilateral salpingo-oophorectomy (BSO) is performed and the Subject does not plan to use Hormone Replacement Therapy within 1 month of the surgery date.
- The subject becomes pregnant.

- The subject has (SGPT/ALAT) or SGOT/ASAT elevation > 5 times the upper limit of normal confirmed upon repeat during the Treatment Period.
- The subject's legally acceptable representative decides to withdraw consent for any reason.
- Heavy menstrual bleeding during the Treatment Period that requires a blood transfusion at any time after having taken 28 days of study drug. If a subject has a blood transfusion during the Post-Treatment Period, the AbbVie TA MD should be contacted to determine if the subject can remain in the study.
- Any other medical reason that AbbVie or the study investigator deems appropriate.

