3.0 Introduction

This statistical analysis plan (SAP) describes the planned statistical analyses for elagolix (ABT-620) Study M12-815 titled "A Phase 3 Study to Evaluate the Efficacy and Safety of Elagolix in Combination with Estradiol/Norethindrone Acetate for the Management of Heavy Menstrual Bleeding Associated with Uterine Fibroids in Premenopausal Women." The analysis plan was created based on the Study Protocol M12-815 Amendment 3 dated 25 September 2017.

This analysis plan describes both the efficacy and safety analyses. The pharmacokinetic data will be analyzed separately and is not addressed in this SAP.

The SAS System 9.2 or above will be used to perform the statistical analyses. All statistical tests will be two-sided and a significance level of 0.05 will be used unless otherwise specified.

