4.3 Sample Size

Approximately 400 subjects will be randomized in a 1:1:2 ratio to placebo (N = 100), elagolix 300 mg BID (N = 100), or elagolix 300 mg BID plus E2/NETA (N = 200). The sample size will provide at least 90% power to detect a difference between the elagolix 300 mg BID plus E2/NETA group and the placebo group in the percentage of subjects with menstrual blood loss (MBL) volume < 80 mL during the Final Month (as defined in Section 7.2) and 50% or greater reduction in MBL volume from Baseline to the Final Month under the assumption of responder rates being 60% and 30% for elagolix 300 mg BID plus E2/NETA and placebo, respectively. The sample size determination is primarily driven by the need for a sufficient number of patients for the safety database. The above sample size was calculated using nQuery advisor 7.0.

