11.2 Primary Efficacy Analysis

11.2.1 Primary Efficacy Endpoint

The primary endpoint will be the percentage of responders, defined as subjects meeting the following two conditions:

- MBL volume < 80 mL at the Final Month (the last 28 days prior to and including the Reference Day), and
- 50% or greater reduction in MBL volume from Baseline to the Final Month (the last 28 days prior to and including the Reference Day)

Subjects who prematurely discontinue study drug due to "lack of efficacy," "requires surgery or invasive intervention for treatment of uterine fibroids," or adverse events will be considered as non-responders. Only primary discontinuation reason is considered.

Baseline MBL volume is defined in Section 7.1.

Final Month is defined as in Section 7.2. If a subject has less than or equal to 28 days of treatment prior to and including the Reference Day, then the Final Month will be the interval between Day 2 to the Reference Day. The AH data on Day 1 will be included in the Baseline MBL volume calculation (provided it is part of a qualifying menstrual cycle) and will not be included in post-baseline MBL volume calculation.

[figure not shown]

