(change or percent change from Baseline), the covariance structure converging to the best fit, as determined by the smallest value for the Akaike Information Criterion (AIC), will be used as the covariance structure in the MMRM analysis for that efficacy parameter. This analysis will be used for the ranked secondary efficacy endpoints: change from Baseline in MBL volume to Month 6, Month 3, and Month 1.

Each of the two response criteria that are components of the primary endpoint, i.e., (1) MBL volume of < 80 mL at the Final Month; and (2) 50% or greater reduction in MBL volume from Baseline to the Final Month will be analyzed separately in the same way as for the primary analysis. Baseline and Final Month MBL volumes obtained for the primary analysis will be used. The number and percentage of subjects meeting each criteria at the Final Month will be summarized by treatment group. The comparison between each elagolix dose group and placebo will be made using a logistic regression model including treatment as the main effect and Baseline MBL volume as a covariate.

Besides the method in the primary analysis, the number and percentage of subjects meeting each criterion at the Final Month will also be analyzed in the same way as in each sensitivity analysis for the primary endpoint, and in the analysis for subjects identified in the adenomyosis subset of interest.

The number and percentage of subjects satisfying either (1) MBL volume < 80 mL, or (2) 50% or greater reduction in MBL volume from Baseline, or both will be summarized for every 28-day interval by treatment group based on observed MBL volume.

Plots will be provided by treatment group using the MBL volume data for the primary analysis (multiple imputation):

- Cumulative distribution function for MBL volume at Final Month;
- Cumulative distribution function for percent change from Baseline to Final Month in MBL volume;
- Proportion of responders at Final Month;

- Cumulative distribution function for change from baseline to Final Month in MBL volume.

Plots will be provided by treatment group using observed MBL volume data:

- Cumulative distribution function for change from baseline in MBL volume to Month 1, 3, and 6;
- Mean change in MBL volume over time.

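### A woman who stops for an adverse event can fail the primary endpoint yet succeed on ranked endpoint 2 (suppression of bleeding), and no sensitivity analysis shows the effect

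*SAP*

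**What the plan says.** **Primary endpoint.** SAP 11.2.1 lists three primary reasons for stopping study drug: lack of efficacy, surgery or invasive intervention for fibroids, "or adverse events will be considered as non-responders". SAP 11.2.2.1, step 3, applies this whether the Final Month blood loss is observed or missing. SAP 11.2.3 keeps the rule in the sensitivity analyses unless stated otherwise; analysis 1 is the one that sets it aside. Under SAP 11.3.1, each of the two component criteria "will be analyzed separately in the same way as for the primary analysis".

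**Suppression of bleeding.** This is second of six ranked secondary endpoints (SAP 11.3), tested in fixed sequence (SAP 11.4). SAP 11.3.2.2 defines success as no bleeding days in the 28 days to the Reference Day, with the window starting no earlier than Study Day 11. A bleeding day is one with more than 2 mL (SAP 7.6.2). The Reference Day is the woman's own last treatment visit or, in some cases, her last dose date (SAP 7.2). On who is analysed, the section says: "The suppression of bleeding analysis will include subjects with at least 38 days prior to and including the Reference Day". It sets no condition on why a woman stopped.

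**Elsewhere.** SAP 11.1, SAP 11.4 and Protocol 8.1.7.2.1 supply no such condition. Protocol 5.3.3.1 and 8.1.7.1.1 state the non-responder rule for the primary endpoint only. SAP 5.1 assigns the full analysis set (all randomized women with at least one dose) to every efficacy analysis.

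**The concern.** Both endpoints are binary, both are read over the Final Month, and both carry confirmatory weight. The primary treats stopping for intolerance or treatment failure as failure. The suppression endpoint ignores the reason for stopping.

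Because the Final Month moves with the woman's own last treatment visit, early stopping does not remove her chance of success once she has 38 days. The natural discordant case is a woman who tolerates the drug badly but is not bleeding when she stops.

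If such women are more common on elagolix than on placebo, the suppression difference is larger than it would be under the primary endpoint's rule. Suppression also gates ranked endpoints 3 to 6. For the primary endpoint, ignoring the reason for stopping is a sensitivity analysis. For suppression it is the only analysis, with no stated justification and no alternative beside it.

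**Working it through.** **1. The plan's own figure.** The only design calculation is for the primary endpoint: "The sample size will provide at least 90% power to detect a difference", with assumed rates of 60% and 30% (SAP 4.3), 200 against 100 women, two-sided 0.05.

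- Pooled rate = (120 + 30)/300 = 0.50; null SE = √(0.25 × (1/100 + 1/200)) = 0.0612.
- Alternative SE = √(0.3 × 0.7/100 + 0.6 × 0.4/200) = 0.0574.
- Power = Φ((0.30 − 1.96 × 0.0612)/0.0574) = Φ(3.13) ≈ 99.9%.

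The stated lower bound is met. It says nothing about suppression, for which the documents give no rate, power or dropout figure.

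**2. The two rules applied to the same woman.** The 38-day limit follows from the window: a 28-day window starting on Day 11 ends on Day 11 + 27 = Day 38.

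| Stops mainly for an adverse event | Primary (11.2.1; 11.2.2.1 step 3) | Suppression (11.3.2.2) |
|---|---|---|
| Reference Day 90, no day above 2 mL on Days 63–90 | Non-responder | Success: at least 38 days, 0 bleeding days |
| Reference Day 90, one or more days above 2 mL in that window | Non-responder | Not suppressed |
| Reference Day 30 | Non-responder | Not in the analysis |

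The first row is the inconsistency. The third row departs from the full analysis set named in SAP 5.1, and a remedy for the first row alone would leave it in place.

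**3. What drives the size.** Let S be an arm's suppression rate, d the share stopping for the three reasons, and e the share of those stops before Day 38. Assume women who stop are bleeding-free at their arm's rate.

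- Discordant women = N × d × (1 − e) × S.
- Rate with the non-responder rule in all treated women = S × (1 − d).

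Every input below is an assumption, chosen to show dependence and not to predict. S is 50% (active) against 5% (placebo), or 20% against 10%. The pairs of d run from 5% in both arms to 15% against 10%, and e from 0 to 50%.

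- Discordant on elagolix plus E2/NETA: from 200 × 0.05 × 0.5 × 0.20 = 1 to 200 × 0.15 × 1 × 0.50 = 15.
- Discordant on placebo: from 100 × 0.05 × 0.5 × 0.05 ≈ 0.1 to 100 × 0.10 × 1 × 0.10 = 1.
- A 45-point difference becomes 47.5 − 4.75 = 42.75 points at the low end of d, and 42.5 − 4.5 = 38.0 at the high end.
- A 10-point difference becomes 19.0 − 9.5 = 9.5 points, or 17.0 − 9.0 = 8.0.

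**4. What the documents offer on direction.** Protocol 3.2.2 names hot flush, headache and nausea as the events that most often led to discontinuation across the programme (1.0%, 0.4% and 0.5%, over mixed doses and durations). In Phase 2b Cohort 1, hot flush was 10.8% on elagolix 300 mg BID with standard-dose E2/NETA and 3.1% on placebo. Protocol 3.2.3 gives 79% meeting the composite bleeding endpoint on that combination. These make bleeding-free stops for intolerance plausible on the active arm. They give neither the stopping rate in this trial nor the share of those women who would be suppressed.

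**The case against.** **It is a specified choice.** The protocol confines the rule to the primary endpoint and defines suppression by bleeding days alone; the SAP follows it. The primary asks about treatment success, and suppression asks about bleeding status while on treatment. The other ranked endpoints carry no such rule either. This stands in part: there is no protocol–SAP contradiction, and an on-treatment strategy can be defended. But the plan does not state or defend one. The blood-volume endpoints are continuous and have no failure category, and haemoglobin is read in a fixed Month 6 window. Suppression, like the primary, is binary with a moving window, so the rule transfers directly.

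**The conflict is conditional.** It needs at least 38 days and no bleeding day in the last 28. Women stopping for lack of efficacy will seldom qualify. This stands; adverse-event stops are the realistic group.

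**Surgery.** A reader might infer that a woman could be credited with suppression that an operation produced, since Protocol 5.4 lists "other procedures including hysterectomy, myomectomy, uterine artery embolization, high intensity focused ultrasound (HIFU), endometrial ablation" among the grounds for withdrawal. The documents do not support building on that.

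- Withdrawal is triggered when surgery is required, not when it has been done.
- The bleeding questionnaire covers the time since the last study visit, and visits are 28 days apart, so a No also covers days before any operation.
- The discontinuation visit is preferably 2 to 7 days after the last dose (Protocol 5.4.1).
- On the natural reading of SAP 7.4.1 and 7.4.3, a questionnaire taken more than 3 days after the last dose is excluded.

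**Failures are visible elsewhere.** These women count as failures on the primary, and SAP 9.0 tabulates reasons for stopping by arm. That is true, but neither table shows what the suppression result would be without them.

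**Conclusion.** The point holds as an inconsistency. Followed as written, the plan can count the same adverse-event discontinuer as a non-responder on the primary endpoint and a success on ranked endpoint 2, with nothing pre-specified to show how much that matters.

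Its size cannot be derived from the documents. The figures in the working rest wholly on assumed suppression and stopping rates. The direction is conditional: it favours elagolix if more women there stop for adverse events while bleeding-free, which is plausible but not shown.

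A reader might go further and conclude that the suppression result would be materially inflated, or its significance manufactured. Nothing in the documents supports that. The point deserves correction because the endpoint is confirmatory and the change is cheap.

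**What to change.** In SAP 11.3.2.2, add that women who prematurely discontinue study drug with a primary reason of adverse event, lack of efficacy, or surgery or invasive intervention for fibroids are counted as not having achieved suppression, whatever their bleeding data. Say explicitly that this includes those who stop before Day 38, who stay in the denominator as members of the full analysis set. Keep the current on-treatment version as a sensitivity analysis.

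If the sponsor prefers the on-treatment version as the main analysis, the minimum is to state that strategy, justify it, and pre-specify the non-responder version as a sensitivity analysis.

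Carrying the rule over to amenorrhea and control of bleeding is optional, since neither is ranked. How to treat women with fewer than 38 days who stop for other reasons is a separate question that this sentence does not settle.

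The cost is one or two sentences and a flag that already exists for the primary endpoint. The downside is a slightly lower reported suppression rate.

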Appendix G. Uterine Bleeding Questionnaire (UBQ) – Treatment Period – SAMPLE

(To be Completed by Site Staff)

Version 2.0

During site visits in the Treatment Period, subjects who **did not** return a Sanitary Product Collection Keg (for menstrual blood loss analysis) will be asked whether they had any uterine bleeding or spotting since their last study visit.

[figure not shown]
1. Did the subject have any bleeding or spotting since her last study visit?

 \Box No \Box Yes

If yes, why were sanitary products not collected/returned? (Please select one response)

- □ Subject only had spotting that did not require the use of sanitary products*
- $\hfill\square$ There was no visible blood on sanitary products*
- □ Subject forgot to/did not collect*
- □ Subject/Site discarded the sanitary products*
- $\hfill\square$ Subject is still bleeding/spotting; will return when bleeding/spotting complete
- □ Subject collected sanitary products and did not bring them to this visit; will return sanitary products at a later date
- \Box Other

* If this response is checked, remind subject to collect and return all used or worn sanitary products with or without visible blood.

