7.6.1.1 Observed MBL Volume Over a Window

If there were observed AH data between two study visits (Product Collection Visit or site visit with UBY completed), then the MBL volume on the days with observed AH data will be the observed AH data and the MBL volume for the rest of days between the two study visits will be imputed as 0 by AH data.

UBQ responses indicate if a subject has any bleeding or spotting since the last study visit (Product Collection Visit or site visit with UBQ completed). If observed evaluable AH data is available over a window, then the UBQ will not be used.

If the AH data is reported as "NVB" (no visible blood, discarded without assay), "NO BLEED" (no collection due to no bleeding as indicated by subject or clinical site on assay requisition form), or "TL BQL" (total below low limit of quantitation), the numeric value for the AH data will be imputed as 0. If the AH data is reported as other character value ("NULL," "IN ERROR," "NO DATA," and etc.), the corresponding numeric value for the AH data will be set as missing.

The observed MBL volume over a window (such as the Final Month, Month 1 [Study Days 2 – 28], Month 2 [Day 29 – Day 56], Month 3 [Day 57 – Day 84], Month 4 [Day 85 – Day 112], Month 5 [Day 113 – Day 140], and Month 6 [Study Days 141 – 168]) is defined as follows:

- If a subject has any evaluable AH data reported in the window, then the subject's MBL volume in this window will be the total combined observed AH data of validated and non-validated sanitary products over this window.
- If a subject is missing AH data or all AH data are unevaluable in the window and the UBQ is completed and indicates no bleeding or spotting, "Subject only had spotting that did not require the use of sanitary products" or "There was no visible blood on the sanitary products" and covers this window, then:

A value of 0 will be assigned to the MBL volume over this window.
- If a subject is missing AH data or all AH data are unevaluable in the window and the UBQ is completed with no bleeding or spotting or "Subject only had spotting that did not require the use of sanitary products" or "There was no visible blood on the sanitary products" indicated but UBQ does not cover the full window, then:

A value of 0 will be assigned to the MBL volume over this window if the days not covered by UBQ response as described above have AH imputed MBL volume (see first paragraph in Section 7.6.1.1) being 0 for those days.

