11.3 Ranked Secondary and Other Efficacy Analyses

Ranked secondary efficacy endpoints during the Treatment Period include the following in the order specified below:

1. Change from Baseline in MBL volume to the Final Month;
2. Percentage of subjects with suppression of bleeding (no bleeding allowed, spotting allowed) at the Final Month;
3. Change from Baseline in MBL volume to Month 6;
4. Change from Baseline in MBL volume to Month 3;
5. Percentage of subjects with Baseline hemoglobin ≤ 10.5 g/dL who have an increase in hemoglobin > 2 g/dL at Month 6;
6. Change from Baseline in MBL volume to Month 1.

Other efficacy endpoints during the Treatment Period include the following:

- Change and percent change from baseline in MBL volume;
- Percentage of subjects with MBL volume < 80 mL and 50% or greater reduction in MBL volume from baseline during 28-day intervals throughout the Treatment Period;
- Percentage of subjects with amenorrhea;
- Percentage of subjects with control of bleeding;
- The number of bleeding days;
- Change and percent change from baseline in hemoglobin concentration;
- Patient Global Impression of Change (PGIC) questionnaire for Menstrual Bleeding and Non-Bleeding Uterine Fibroid Symptoms;
- Change and percent change from baseline in fibroid and uterine volume;
- Change from baseline for the UFS-QoL;
- Change from baseline for the EuroQoL-5D (EQ-5D-5L);
- The Health Care Resource Utilization (HCRU) questionnaire;
- Change from baseline for the WPAI.

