11.4 Handling of Multiplicity

The primary comparison for all analyses will be made between elagolix 300 mg BID in combination with E2/NETA and placebo. The elagolix 300 mg BID alone group serves as a reference arm.

Therefore, no adjustment of the type I error rate (alpha) for primary analysis of the primary endpoint is needed. Ranked secondary endpoints will follow a fixed-sequence testing procedure.¹¹

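### The suppression-of-bleeding rule (ranked endpoint 2) accepts a favourable UBQ without requiring it to cover the 28 days, so a woman with a partly unobserved Final Month can count as a success

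*SAP*

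**What the plan says.** Suppression is the second of six ranked secondary endpoints in SAP Section 11.3: "Percentage of subjects with suppression of bleeding (no bleeding allowed, spotting allowed) at the Final Month". Section 11.4 adds: "Ranked secondary endpoints will follow a fixed-sequence testing procedure". Endpoints 3 to 6 can therefore be tested formally only if endpoint 2 succeeds.

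Section 11.3.2.2 fixes the analysis set: "The suppression of bleeding analysis will include subjects with at least 38 days prior to and including the Reference Day". It then covers women without usable blood-loss data: "If a subject did not have evaluable AH data during the last 28 days and no bleeding was indicated on UBQ" (spotting-only and no-visible-blood answers are accepted), "then the subject is considered having achieved suppression of bleeding". It states no coverage condition and does not refer to Section 7.6.1.1.

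The UBQ has no fixed recall period. Protocol Appendix G asks: "Did the subject have any bleeding or spotting since her last study visit". It is completed only at visits where no keg is returned.

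Section 7.6.1.1, which supplies the volume for the primary endpoint, separates two situations. A favourable UBQ that covers the window gives 0 mL. Where the favourable answer is "indicated but UBQ does not cover the full window", 0 mL is assigned only "if the days not covered by UBQ response as described above have AH imputed MBL volume" equal to 0. Otherwise the volume is missing, and Section 11.2.2 sends it to multiple imputation.

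**The concern.** The SAP recognises in one place that a UBQ may describe only part of a 28-day window and treats such evidence as insufficient. In Section 11.3.2.2 the same evidence is sufficient for success.

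Suppression means no bleeding day in 28 days (Protocol Section 8.1.7.2.1), and an answer about part of that time cannot establish it. The departure goes one way only, from missing to success, on an endpoint that gates four others. Sections 11.3.2.1 (amenorrhea), 11.3.2.3 (control of bleeding) and 11.3.3 (bleeding days) also lack a coverage condition.

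**Working it through.** The documents give no figure for this endpoint to reproduce. The only power statement concerns the primary endpoint and has no bearing here. The check is to apply both rules to the same woman.

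**Inputs**

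- Final Month (SAP 7.2): 28 days up to and including the Reference Day. For Reference Day 168 it starts on 168 − 28 + 1 = Day 141.
- Visit windows (Protocol Table 1): Month 5 is 140 ± 4, or Days 136 to 144. Month 6 is 168 − 4 to 168 + 6, or Days 164 to 174.
- UBQ (Protocol 5.3.1.1 and Appendix G): given only when no keg is returned; asks about the time since the last visit.
- AH data (SAP 7.6.1.1): results reported as errors or as no data are set to missing. Where AH data were observed between two visits, the other days between those visits become 0.

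**Case 1: unevaluable keg.** Month 5 visit on Day 140. Product Collection Visit on Day 152 with a keg, all results unevaluable. Month 6 visit on Day 168 without a keg; UBQ answer is no bleeding or spotting.

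- Days covered by the UBQ: 153 to 168, which is 168 − 153 + 1 = 16.
- Days not covered: 28 − 16 = 12 (Days 141 to 152). A keg came in on Day 152, so no UBQ was due. No AH data were observed between Days 140 and 152, so no zeros are created.
- Section 7.6.1.1: missing, then multiple imputation.
- Section 11.3.2.2: no evaluable AH data, no bleeding on the UBQ, so suppressed.

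The protocol places a Product Collection Visit within about 5 days after the last product was collected. Here that is about Day 152 − 5 = 147 or later, inside the window. Bleeding in the uncovered days is therefore plausible. It is not established, because spotting and unstained products are also returned.

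**Case 2: full coverage.** The UBQ covers Days 141 to 168. Section 7.6.1.1 gives 0 mL and Section 11.3.2.2 gives suppressed. The rules agree.

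**Case 3: short visit interval only.** Month 5 visit on Day 144, Month 6 visit on Day 164, so the window is Days 137 to 164. The last UBQ covers 164 − 144 = 20 days, which leaves 28 − 20 = 8 (Days 137 to 144). If those 8 days are zeros from AH data, or a favourable UBQ at Month 5 covers them, Section 7.6.1.1 gives 0 mL and Section 11.3.2.2 gives suppressed. The rules agree.

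**Size per woman.** With planned arm sizes as denominators, one such woman moves the suppression rate by 1/100 = 1 percentage point on placebo or elagolix alone, and by 1/200 = 0.5 point on the combination. The 38-day requirement can make the true denominators somewhat smaller.

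**The case against.** The strongest reply is that the gap is nearly closed already. At each treatment visit a woman either returns a keg or answers the UBQ, so days that the last UBQ does not reach were normally dealt with at the visit before. This stands. A reader might infer that any short interval between visits produces a false success; Case 3 shows that it does not. What remains is mainly the wholly unevaluable keg.

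A second reply is that coverage is implied, because suppression is defined over 28 days and the rule mentions the last 28 days. This does not stand. In the rule, those words qualify the AH data and not the UBQ, and where the SAP wants coverage it says so.

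A reader might also infer that known bleeding becomes success: a woman reports uncollected bleeding at one visit in the window and none at the next. The text does not support this. On its natural reading, a UBQ in the window that reports bleeding means that bleeding was indicated. Section 11.3.2.3 says expressly that such a report fails its criterion, and Section 11.3.3 tabulates women without evaluable AH data whose UBQ indicated bleeding. Section 11.3.2.2 does not say how conflicting UBQs are resolved, which is worth clarifying, but the point does not rest on it.

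Finally, different status on two endpoints is not in itself an error. Suppression has its own analysis set, an unadjusted test and no multiple imputation. That is fair. The fault is that success is declared on evidence that leaves part of the window unobserved.

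**Conclusion.** The point holds in a narrow form. Followed as written, Section 11.3.2.2 counts a woman as suppressed when part of her last 28 days has neither a favourable UBQ nor a zero from AH data, while Section 7.6.1.1 treats the same Final Month as missing.

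The conclusion rests on the literal wording and on one assumed event: a keg handed in during the window with no evaluable result, no other evaluable AH data in the 28 days, and a later favourable UBQ. The documents give no frequency for this. The number is unknown and probably small.

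It is tempting to go further and say that the rule favours active treatment or endangers the testing of endpoints 3 to 6. The documents do not support that. The rule applies alike to all arms, and nothing given allows an effect on the between-arm difference or the test to be calculated. This is a minor correction, worth making because the endpoint is ranked and gates others.

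**What to change.** Add to Section 11.3.2.2 that a woman without evaluable AH data in the last 28 days is counted as suppressed only if favourable UBQ responses, together with days set to 0 from AH data under Section 7.6.1.1, span all 28 days. State that women in the analysis set who remain unresolved are counted as not having achieved suppression.

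The second sentence is a choice, and a conservative one. It matches the non-responder sensitivity analysis in Section 11.2.3, but the primary analysis would still impute these women. The coverage condition is the essential part.

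Apply the same condition in Sections 11.3.2.1 and 11.3.2.3 before counting a success, and in Section 11.3.3 before recording 0 bleeding days. Women in Cases 2 and 3 keep their status.

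The cost is about a sentence in each section. The coverage derivation is already needed for the primary endpoint, and no new data are collected. The downside is a slightly lower suppression rate if such women occur.
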